In addition it has been noted in the literature that there may be genotypic and phenotypic differences between prostate carcinoma recurrence in the prostate bed and in extraprostatic nodal locations. Exome sequence analyses of prostate cancer metastases have identified mutations specific to castrate-resistant metastases including components of the Wnt pathway [7], while microarray studies have identified changes in gene expression specific to bone metastases including IGFBP2, WHSC2, and CRIM1 [8]. Integrative copy number and gene expression analyses have also identified important differences between primary and metastatic lesions including components of the AR pathways such as NCOA2 [9] and the polycomb complex chromatin suppressor EZH2 [10].

Imaging has the potential to play a central role in the detection of recurrent prostate carcinoma and in the differentiation of prostatic from extraprostatic recurrence. Yet to date, **no one method has demonstrated definitive accuracy in this regard.** For this reason, newer methods such as diffusion weighted MR (DWMR) and positron emission tomography (PET) with molecular radiotracers are currently under study for the characterization of post therapy recurrence [11-19]. Each of these techniques has its own strengths and weaknesses and each interrogates only a portion of the anatomic and imaging biomarker data present in recurrent prostate carcinoma.

The specific hypothesis in this proposal is that a combination of molecular interrogation with the synthetic amino acid PET radiotracer *anti*-[¹⁸F]FACBC PET-CT combined with multiparametric MR including DWMR will provide a greater degree of imaging biomarker data than each technique individually. We believe that such transmolecular interrogation will enable us to more accurately diagnose recurrent prostate carcinoma within the prostate bed and in extraprostatic locations. We can then utilize tissue obtained from this study to examine the second specific hypothesis that there are genotypic differences between prostate carcinoma recurrence confined to the prostate bed and those that are extraprostatic, and also be useful to elucidate amino acid transport uptake mechanisms of *anti*-[¹⁸F]FACBC.

A. Background and Significance

One in six men will develop prostate cancer [20]. Due to the widespread use of PSA testing, cancer is often detected before systemic disease occurs [2]. Depending on clinical presentation, therapy is typically approached through locally directed interventions such as radical prostatectomy, brachytherapy, external beam radiotherapy or cryotherapy. Yet, approximately, 30% of patients treated with definitive local therapy experience recurrent disease [2, 3].

Recurrent disease usually manifests with rising PSA. The differentiation of local from extraprostatic recurrence is of critical importance since salvage techniques can cure disease confined to the prostate bed. If pelvic nodal involvement is suspected, radiation fields can be extended to include the pelvic nodes [4-6]. Systemic disease is treated with hormonal manipulation and/or chemotherapy. PSA level is not useful in the differentiation of local from extraprostatic recurrence, though the rate of PSA rise may have some value [21].

Imaging plays a central role in the detection of recurrent prostate carcinoma in the prostate bed and in the differentiation of prostatic from extraprostatic recurrence. Conventional methodology including computed tomography (CT), magnetic resonance imaging (MR), transrectal ultrasound, bone scan and ¹¹¹Indium-capromab-pendetide (ProstaScint) (EUSA Pharma, Langhorne, PA) may provide important information, but suffer from less than optimal diagnostic performance [22-30]. Newer methods such as diffusion weighted MR (DWMR) and positron emission tomography (PET) with molecular radiotracers are currently under study for the characterization of post-therapy recurrence [11-19]. MR with superparamagnetic (USPIO) particles has shown promise but is not available in the US [19]. The sensitivity of most imaging techniques is dependent upon PSA level, doubling time, and velocity [16, 31, 32].

One PET radiotracer which has shown promise in the staging and restaging of patients with prostate carcinoma is *anti*-1-amino-3-[¹⁸F]fluorocyclobutane-1-carboxylic acid (*anti*-3-[¹⁸F]FACBC) which is a synthetic amino acid analog with little renal excretion and transport via sodium dependent and independent pathways [33-35]. In a recent study, *anti*-3-[¹⁸F]FACBC demonstrated higher accuracy compared with ¹¹¹Indium-capromab-pendetide in the restaging of patients with suspected recurrent prostate carcinoma [36]. Yet there was suboptimal specificity in the prostate bed, especially after non-radical prostatectomy therapy. It is not yet clear if this was the result of sampling error during biopsy and/or nonspecific uptake by *anti*-3-[¹⁸F]FACBC in non-neoplastic tissue.

In one study of patients with both primary and recurrent prostate carcinoma, DWMR demonstrated significant differences of mean apparent diffusion coefficients (ADC) between malignant and benign nodes with an accuracy of 85.6% (sensitivity 86%, specificity 85.3%) compared with an MR accuracy of 66.1% based on nodal size alone. Yet there was significant overlap of individual ADC values between benign and malignant foci [18]. In addition, less than 50% of patients had histologic follow-up and 6 month follow-up was accepted as truth in those without histologic confirmation. In another recent study in patients with suspicion of recurrence after high dose brachytherapy, DWMR was noted to have a sensitivity of 68% and a specificity of 95% in the detection of tumor in the prostate bed [37]. Multiparametric MRI achieved the highest sensitivity (77%) but with slightly decreased specificity (92%).

Thus, there may be utility in combining both multiparametric MR and synthetic amino acid PET as a hybrid transmolecular technique in the detection and restaging of recurrent prostate carcinoma. The data from this study could be used to design a more comprehensive study that would lend itself to novel PET-MR hybrid devices which are now commercially available.

There may also be genotypic and phenotypic differences between prostate carcinoma recurrence in the prostate bed and in extraprostatic nodal locations. Exome sequence analyses

of prostate cancer metastases and integrative copy number and gene expression analyses have identified mutations specific to specific metastases [7, 8]. Other authors have also identified important differences between primary and metastatic lesions including components of the AR pathways such as NCOA2 [9] and the polycomb complex chromatin suppressor EZH2 [10].

Furthermore, we have determined in RT-PCR analysis of primary and recurrent prostate carcinoma and distant metastases that the amino acid transport (AAT) proteins PAT1, LAT2 and ASCT2 as well as LAT1, xCT, LAT3 and ASCT1 are associated with malignancy. In analysis of lymph node metastases only, LAT1 and ASCT1 drop below significance. In addition, out of the AATs which were associated with malignancy, PAT1 had the highest correlation co-efficient of significance of expression to *anti*-3-[¹⁸F]FACBC uptake [38].

A. Specific Aims

Aim 1. Investigate the ability of *anti*-[¹⁸F]FACBC PET-CT and multiparametric/DW MRI imaging individually then together to detect local and extraprostatic recurrence of prostate cancer.

We will undertake a preliminary clinical trial with 25 patients post-definitive non-prostatectomy therapy for prostate carcinoma and who have suspected recurrence based on elevated PSA greater than nadir plus 2 ng/ml with absolute PSA \geq 4.0 ng/ml with any doubling time (DT) or with PSA 2.0-3.99 ng/ml with DT \leq 10 months. We will perform *anti*-[¹⁸F]FACBC PET-CT with early and delayed imaging, as well as multiparametric/DW MRI. Each study will be blindly interpreted then fused utilizing software registration and co-interpreted. Data from both studies will be used to direct biopsies to areas of concern in the prostate bed, and in extraprostatic locations. Results will be compared to the standard of pathologic analysis of prostate bed biopsies as well as clinical follow-up. The diagnostic performance of *anti*-[¹⁸F]FACBC PET-CT and multiparametric/DW MRI will be assessed individually then together. We will also determine if there is correlation between synthetic amino acid PET and MR, such as SUV and apparent diffusion co-efficient (ADC).

Rationale for AIM 1.

As has been outlined in the Preliminary Results section of this proposal, *anti*-[¹⁸F]FACBC has been demonstrated to 1) have high sensitivity in the detection of recurrent prostate carcinoma though with suboptimal specificity in the prostate bed, and 2) the ability to differentiate prostatic from extraprostatic recurrence with high accuracy. *anti*-[¹⁸F]FACBC may thus have specific advantages for imaging recurrent prostate neoplasia within a clinical setting over conventional imaging. Yet, MR, especially with the addition of diffusion weighted imaging, has been reported in preliminary studies to provide high accuracy especially in the characterization of prostate bed recurrence. We hypothesize that utilization of a transmolecular approach combining synthetic amino acid radiotracer PET imaging with multiparametric MR has the potential to identify the presence and location of recurrent prostate carcinoma to a higher accuracy than either modality alone. **Therefore the most comprehensive manner to assess our hypothesis that PET-CT imaging with *anti*-[¹⁸F]FACBC in combination with multiparametric MR will lead to improved patient care resulting from detection of local and distant recurrent disease (Specific Aim #1) is to undertake a prospective clinical trial designed to address these issues.**

Secondary Aims

Aim 2. To determine mRNA differences between prostate carcinoma recurrent in the prostate bed and extraprostatic locations and to correlate any difference with quantifiable imaging biomarker data such as SUV for *anti*-[¹⁸F]FACBC PET-CT and ADC for MR.

Within the structure of the clinical trial (the same 25 patients) we will obtain sufficient tissue to perform mRNA sequencing on samples to exploit differences between the genetic profiles of recurrent prostate carcinoma in the prostate bed versus metastases. Since approximately 30% of patients with PSA > 4 ng/ml by our experience manifest with both prostate bed and nodal recurrence, we believe at least 8-10 patients in whom this comparison can be directly made will be available for analysis. This may also occur with lower PSA levels with faster DT. We will then correlate any differences in genotypic profile with imaging biomarkers from synthetic amino acid PET and MR, such as SUV and ADC.

Sub-aim 2a. To evaluate protein expression of previously identified amino acid transporters (AATs) that have been implicated in the uptake of *anti*-[¹⁸F]FACBC.

Also within the context of the clinical trial of 25 patients, we will, whenever there is sufficient tissue, determine if candidate amino acid transport (AAT) proteins identified from data obtained in an earlier study (Project 1: P-50 ICMIC) are expressed. We will perform IHC analysis of up to 7 candidate AAT or co-transporters, specifically PAT 1, LAT1, LAT2, 4F2hc, and ASCT2, LAT3 and ASCT1 to understand if the AAT whose mRNAs are increased in malignant prostate carcinoma and correlated with *anti*-[¹⁸F]FACBC uptake are expressed at the protein level by IHC analysis.

Rationale for Aim 2 and Sub-aim 2a.

As has been outlined in the Preliminary Results section of this proposal, there is preliminary data in the literature of gene expression and mutational differences between primary prostate carcinoma cells and those prostate metastases [7-9] as well as between bone metastases and non-osseous metastases [8]. We propose within the context of this clinical trial to provide tissue to further understand these differences both in the ability of prostate carcinoma to transport and retain amino acids measured as uptake of *anti*-[¹⁸F]FACBC and expression characteristic as studied by multiparametric MR such as ADC parameters on DWMR and uptake and retention of Gadolinium. If we can determine that there are gene expression differences between malignancy confined to the prostate bed and those that are extraprostatic, we can correlate these differences to PET uptake and MR appearance. Furthermore, we may also be able to derive incidental genotypic information that could be exploited on subsequent unrelated experiments. In addition, we have preliminary evidence based on our earlier research that PAT1, LAT2 and ASCT2 as well as LAT1, xCT, LAT3 and ASCT1 were associated with malignancy. Out of the AATs that were associated with malignancy, PAT1 expression had the strongest correlation coefficient relative to *anti*-3-[¹⁸F]FACBC uptake [38]. We believe that a study such as this one provides an ideal opportunity to obtain both prostatic and extraprostatic tissue from the same patient in order to test these hypotheses using the patient as his own control.

Our rationale for utilizing patients with PSA ≥ 4 is as follows. A total of 127 patients have been studied already in an R-01 study of the diagnostic performance of *anti*-3-[¹⁸F]FACBC versus conventional imaging. If the patients are stratified by PSA level as in the table below, 41/73 were positive in the prostate bed only, 25 in both prostate bed and lymph nodes, and 1 in lymph nodes only. Thus, in the 25 patients whom will be studied in this population,

approximately 23 will be expected to have disease in the prostate bed and approximately 9 will have disease in nodes, most of the latter will also have disease in the prostate bed. This should provide sufficient tissue for the above secondary aims. In addition, we have demonstrated that greater extraprostatic involvement will occur with shorter DT even at lower PSA levels. Thus the addition of PSA 2.0-3.99 ng/ml plus DT \leq 10 months is a reasonable method to increase recruitment while still acquiring tissue from extraprostatic involvement.

PSA group	<4 (n=54)	\geq 4 (n=73)	Total(n=127)
Prostate bed only (+)	27	41	68
LN only (+)	3	1	4
Both	8	25	33
Total	38	67	105

We hypothesize that by identification of disease recurrence in the prostate bed and extra-prostatic locations, we can exploit differences in mRNA analysis to correlate these differences to synthetic amino acid transport as well as MR parameters such as ADC mapping, and also better understand the relationship of AAT protein expression to *anti*-3- ^{18}F FACBC uptake. **Therefore the most comprehensive manner to obtain tissue to test our hypotheses is within the context of this prospective clinical trial.**

[figure not shown]
C1.0 Research Design and Methods (Aim 1)

We will undertake a **clinical trial with 25 patients** who have undergone definitive therapy for prostate carcinoma and who have suspected recurrence based on elevated PSA greater than nadir plus 2 ng/ml with absolute PSA \geq 4.0 ng/ml with any doubling time (DT) or with PSA 2.0-3.99 ng/ml with DT \leq 10 months. We will perform *anti*- ^{18}F FACBC PET-CT with early and delayed imaging as per the detailed protocol below. All patients will also undergo staging including multiparametric MR with diffusion weighted imaging. Other standard of care imaging such as bone scan, ProstaScint, CT, and transrectal ultrasound may also be performed per clinical judgment. These latter studies including MR are standard of care at our institution and will not be charged to the grant. We will investigate the ability of *anti*- ^{18}F FACBC PET-CT imaging to detect recurrence of prostate carcinoma in the prostate bed and in extraprostatic locations validated by pathologic analysis of prostate bed biopsies ideally guided by MR or ultrasound fusion of molecular to anatomic data in the prostate bed and percutaneous or laparoscopic guided biopsies of nodal and skeletal disease. Within the structure of the clinical trial, we will also evaluate the ability of transmolecular imaging with *anti*- ^{18}F FACBC PET-CT and multiparametric MR in the discrimination of prostatic from extra-prostatic recurrence, validated by a combination of pathologic analysis as well as imaging and clinical correlation. Though the grant itself extends for one year, patients may be followed up to 5 years to determine true negative imaging findings at minimal cost. Finally within the context of the clinical trial, tissue will be obtained for Aims 2 and Sub-aim 2a.

C1.1 Anti- ^{18}F FACBC radiolabeling

Methods. Production will be accomplished by the GE FastLab cassette system. Alternatively by automated synthesis developed by [name] and [name] [39] as outlined in Figure 15. The automated radiosynthesis of *anti*- ^{18}F FACBC will be carried out in a chemical process

control unit (CPCU) with a computer interface. The two-step reaction sequence will involve incorporation of no-carrier-added potassium [^{18}F]fluoride into a protected triflate precursor and deprotection using aqueous hydrochloric acid. The crude reaction mix will be passed in series through ion-retardation resin, an alumina-N SepPak[®], an HLB cartridge and a 0.22 μm sterile filter, and the resulting aqueous solution will be collected in a dose vial. The radiochemical purity of the product will be determined by TLC. Additional chemical solvent purity will be measured by Gas Chromatography (GC). The total time for synthesis of *anti*-[^{18}F]FACBC after delivery of [^{18}F]fluoride will be ~ 70 minutes, and the average decay-corrected yield of *anti*-[^{18}F]FACBC will be $24 \pm 4\%$ ($n = 40$ runs, average \pm standard error) in over 99% radiochemical purity. This procedure will provide 140-200 mCi of *anti*-[^{18}F]FACBC at the end of synthesis. We have prepared greater than 100 batch productions for tumor imaging in volunteer subjects.

C1.2 PET-CT imaging protocol to measure amino acid uptake

Methods. PET-CT images will be acquired on a GE Discovery 690 Time of Flight (TOF) 16 slice PET-CT scanner or equivalent. All studies will use measured attenuation correction (routinely acquired through the initial CT portion of the scan). All subjects will be required to fast for four hours to normalize their neutral amino acid levels. Non-strict fasting is not an absolute contraindication and may be overridden on a case by case basis since it is unknown if fasting affects FACBC uptake positively or negatively. One hour prior to scanning, the patient will drink 500 ml of 1.2% (Readi-Cat) oral contrast over 1 hour to maximize conspicuity of abdomen and pelvic structures. IV contrast will not be used. Prior to placement in the tomographic gantry, an intravenous catheter will be placed for injection of tracer. The subject will be placed in the tomograph gantry for completion of the CT scan. Ambient conditions will be a quiet, dimly lit room. *anti*-[^{18}F]FACBC (10 mCi) will be injected into an antecubital vein in a slow bolus infusion over 1-2 minutes. At 5 minutes, 4 consecutive 2.5 minutes per frame acquisitions will be obtained starting from the prostate level of the pelvis and extending superiorly to the diaphragm. At 16 minutes, this process will be repeated. Thus, 4-15.5 minute, and 16-27.5 minute acquisitions from the pelvis extending superiorly to the abdomen at the diaphragm will be obtained (Figure 1). This imaging schema is based on analysis of our data to date in which early and delayed uptake to 30 minutes yields the most diagnostic information. Imaging may be carried out with HD mode and respiratory gating or TOF mode with or without respiratory gating.

[figure not shown]

Figure 1: CT of abdomen and pelvis followed by injection of *anti*-[^{18}F]FACBC then PET scanning as above.

Summary of PET-CT Scanning Procedure

- 1) The patient will be placed in the tomographic gantry for a CT scan of the abdomen-pelvis to be utilized for anatomic imaging and correction of emission data (approximately 1 minute).
- 2) The patient will then receive a bolus of *anti*-[¹⁸F]FACBC injected IV over 1-2 minutes
- 3) The dosage will be approximately 10.0 mCi (3.70 x 10⁸ Bq).
- 4) At 5 minutes after initial injection (3 minutes after injection ceases), a 2.5 minute per bed position PET acquisition will start at the pelvis with the inferior aspect of the acquisition to include the entire prostate or prostate bed.

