Upon completion of the study and/or after additional follow-up, each patient may be re-reviewed by the same Ground Truth Panel to determine if the predicted findings on *anti*-[¹⁸F]FACBC scan and MR individually and in tandem match those of clinical and pathologic findings especially in regard to the identification of prostatic versus extraprostatic recurrence. Also at that time uptake parameters will be reviewed. At no time this study will interfere with proper therapy as determined by the patient's physicians and the patient.

C2.0 Study Design and Methods (Aim2 and Sub Aim 2a)

Rationale. We hypothesize that *anti*-[¹⁸F]FACBC uptake is mediated by a LAT protein subtype or subtypes. However, the precise LAT subtype involved in all cases is unknown. We also further hypothesize that there are genotypic differences between recurrent prostate carcinoma cells confined to the prostate bed and those that are extraprostatic and that these differences can be explored via proper identification of candidate tissue via transmolecular imaging to be performed at termination of study or when sufficient tissue has been collected.

Experimental Design. To test the above hypothesis, we will compare mRNA expression of recurrent prostate carcinoma tissue within the prostate bed and extraprostatic. In addition we will utilize *anti*-[¹⁸F]FACBC avid tissue to confirm that the following AAT subtypes based on preliminary data are expressed at the protein level: PAT 1, LAT1, LAT2, 4F2hc, and ASCT2, LAT3 and ASCT1. We will study 8-10 samples of each recurrent prostate carcinoma in the prostate bed and 8-10 samples of disease outside the prostate bed, preferably in the same patient. We predict that one or more AAT subtypes will be relatively overexpressed by IHC in FACBC-avid carcinoma. We also predict that there will be differences in mRNA expression

based on these tissue samples between disease confined to the prostate bed and those that are extraprostatic. Based upon tissue availability we will perform IHC in the following rank priority: First: PAT 1; Second: LAT1, LAT2, 4F2hc; Third: ASCT2, LAT3 and ASCT1. This priority ranking is based on our desire to first confirm phenotypic expression of PAT1, since presence of this AAT correlated most strongly with *anti*-[¹⁸F]FACBC uptake, followed by LAT1 and LAT2 with the heterodimeric associated protein 4F2hc, and ASCT2, LAT3 and ASCT1.

C 2.1 Quantitative next-generation mRNA sequencing

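### The plan's own rates give about 7.5 to 8.6 paired patients for Aim 2 at best, so neither a minimum of 8 nor a figure of 10 is supported

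*Combined protocol and SAP*

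**What the plan says.** Under Secondary Aims, Aim 2, the tissue comes from the trial's own patients: "Within the structure of the clinical trial (the same 25 patients) we will obtain sufficient tissue to perform mRNA sequencing". The expected yield is then derived from a rate: "Since approximately 30% of patients with PSA > 4 ng/ml by our experience manifest with both prostate bed and nodal recurrence", and so "we believe at least 8-10 patients in whom this comparison can be directly made will be available for analysis". The section adds that the same pattern may occur at lower PSA with faster doubling time, without a figure.

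The Rationale for Aim 2 and Sub-aim 2a gives the counts from the earlier study of 127 men. For PSA of at least 4 ng/ml, "41/73 were positive in the prostate bed only, 25 in both prostate bed and lymph nodes, and 1 in lymph nodes only". For PSA below 4, the table shows 8 of 54 with both sites positive. From these counts the protocol expects about 23 of its 25 men to have bed disease and "approximately 9 will have disease in nodes, most of the latter will also have disease in the prostate bed". It calls admitting men with PSA 2.0-3.99 ng/ml and a doubling time of 10 months or less "a reasonable method to increase recruitment while still acquiring tissue from extraprostatic involvement".

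Section C2.0 sets a target for each site: "We will study 8-10 samples of each recurrent prostate carcinoma in the prostate bed and 8-10 samples of disease outside the prostate bed". It prefers, but does not require, that both come from the same patient. The sample size paragraph in section E claims at least 80% power for a difference of 1 SD, using a two-sided t-test at 0.05 and a sample size of 25.

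**The concern.** The Aim 2 sentence turns a rate into a count, and the count is higher than the rate allows. It also states the count as a minimum, although a rate times a sample size gives an expected value that is often missed. The figure is described as patients available for analysis, but the rates count men with disease at both sites. A man becomes an analysable pair only if both sites are biopsied and both samples qualify. Section C1.7 leaves extraprostatic sampling to clinical judgment and passes tissue to Aim 2 only when there is enough of it. Section C2.1 adds limits on RNA yield, purity and amplification. No allowance is made for these losses.

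At stake is what the mRNA comparison can show. The rationale values the patient as his own control, and at this size one or two pairs change the detectable difference noticeably.

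**Working it through.** **Inputs.** N = 25; stated rate of both sites about 30% (Secondary Aims, Aim 2); both sites 25/73 for PSA ≥ 4, 8/54 for PSA < 4 and 33/127 overall (table in the Rationale for Aim 2); two-sided 0.05, 80% power and 1 SD (Sample size and power calculation).

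**1. Reproduce the plan's projections.** Bed disease, PSA ≥ 4: (41 + 25)/73 × 25 = 22.6, stated as about 23. Nodal disease: (25 + 1)/73 × 25 = 8.9, stated as about 9. Both agree, so the plan applies the PSA ≥ 4 column to all 25 men.

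**2. Expected pairs.** Expected count = N × rate.
- Cited 30%: 25 × 0.30 = 7.5
- Table, PSA ≥ 4: 25 × 25/73 = 8.56
- Table, all PSA: 25 × 33/127 = 6.50

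The first is below 8. The second is between 8 and 9. An expected 10 would need 10/0.30 = 33 or 10/(25/73) = 29 patients.

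**3. Chance of reaching the stated numbers.** Number of pairs taken as binomial(25, p).

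| Rate | Expected | P(fewer than 8) | P(10 or more) |
|---|---|---|---|
| 30% | 7.5 | 51% | 19% |
| 25/73 | 8.6 | 33% | 34% |

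**4. Tissue loss.** The documents give no loss rate. As an illustration only, if 80% of such men yielded a usable pair, the expected count would be 0.80 × 7.5 = 6.0 to 0.80 × 8.56 = 6.8.

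**5. Power if analysed as pairs.** Two-sided paired t-test at 0.05: degrees of freedom n − 1, noncentrality d√n, with d in SDs of the within-pair differences.

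| Pairs | Power at 1 SD | Difference for 80% power |
|---|---|---|
| 7 | 60% | 1.27 SD |
| 8 | 68% | 1.16 SD |
| 9 | 75% | 1.07 SD |
| 10 | 80% | 1.00 SD |

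**6. Power if analysed as unpaired samples.** With the plan's projection of 23 bed and 9 extraprostatic samples, treated as independent: degrees of freedom 30, noncentrality d/√(1/23 + 1/9). Power at 1 SD is 69%, and 80% power needs about 1.14 SD, with SD now that of a single sample. These counts are also before losses.

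**The case against.** The best defence is that the low end of the range does follow from the plan. The table rate gives 8.56, which lies inside 8 to 10, and the shortfall from a rounded 30% is half a patient. The sentence is hedged as a belief, for a secondary aim of a preliminary trial, and the plan acknowledges tissue limits without quantifying them. This stands as far as it goes: 8 or 9 is a fair best-case expectation. It does not rescue the wording as a minimum, or the 10. Even dividing by positive men only gives 25 × 25/67 = 9.3.

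Three stronger readings are tempting, and the documents do not support them.

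- **That the plan's rates imply about 6.6 pairs or fewer.** Giving 40% of the men a PSA below 4, at the 8/54 rate, yields 25 × (0.6 × 25/73 + 0.4 × 8/54) = 6.6. The plan gives no such share. The 8/54 rate also covers every man with PSA below 4, whereas only those with PSA 2.0-3.99 and short doubling time are eligible. The plan says short doubling time goes with more extraprostatic disease.
- **That the number of pairs is the sample size of Aim 2.** Section C2.0 only prefers same-patient tissue, section E2.0 names a t-test or rank sum test, and the power statement uses 25. The paired figures apply only if pairs are analysed. The unpaired figures show that the limit does not vanish otherwise.
- **That the pair count should replace the target in section C2.0.** That target is per site. With about 23 bed-positive men expected, bed samples are not limited by pairs.

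**Conclusion.** The statement is wrong as written, in a limited way. The rate it cites gives 7.5 pairs and the table gives 8.6, so 8 to 9 is the best-case expectation. Neither a minimum of 8 nor a figure of 10 is supported. At those rates, fewer than 8 pairs would occur 51% or 33% of the time, and 10 or more 19% or 34%. In a paired analysis the plan's 80% power for 1 SD is met only at 10 pairs; with 23 and 9 unpaired samples it is 69%.

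These figures assume that all 25 men have PSA of at least 4 ng/ml, that patients are independent with a common rate, and that no pair is lost to biopsy or RNA limits. Admitting lower-PSA men could change the count, but the documents cannot say by how much; the pooled table rate, 6.5, is only a reference point. The rates count nodal disease only. Skeletal samples could add to the extraprostatic total, but no rate is given and men with characteristic bone scan findings are excluded.

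A reader might infer that Aim 2 cannot be carried out. The documents do not support that: they support a smaller expected yield and a larger detectable difference than stated.

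**What to change.** 1. In Secondary Aims, Aim 2, replace the minimum of 8 to 10 with: *about 7-9 patients expected if all have PSA of at least 4 ng/ml, before tissue and RNA losses, with a 33-51% chance of fewer than 8*.
2. Label any allowance for men with PSA 2.0-3.99 ng/ml as a scenario, stating the assumed share and rate. The pooled table rate (6.5 pairs) can be shown for reference.
3. In the sample size paragraph, state the detectable difference at 80% power for the tissue expected: 1.27, 1.16 and 1.07 SD of the paired differences at 7, 8 and 9 pairs, or about 1.14 SD for 23 against 9 unpaired samples. Say which analysis, and which SD, is meant.
4. In section C2.0, keep the bed target and note that the 8-10 extraprostatic samples are limited by about 9 expected node-positive men before losses.

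The cost is wording only, with no change to enrolment or procedures. The stated yield and detectable difference become less favourable.
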